7.1.1 Vital Signs

Baseline vital signs (body temperature, respiratory rate, and heart rate) will be documented within 15 minutes (± 5 minutes) before randomization and at the following time points from the time of randomization: 1, 3 (± 15 minutes), 6, 12 (± 1 hour), 18, 24, 36, and 48 hours (± 2 hours) post-randomization.

Subjects randomized to the active study arm will have additional vital signs (respiratory rate and heart rate) documented every 5 minutes (± 2 minutes) during the administration of lucinactant for inhalation for Dosing Group I and II. For Dosing Groups III and IV, vital signs will be documented every 15 minutes (± 5 minutes) after randomization.

For all dosing groups, subjects randomized to the nCPAP only arm will have additional vital signs (respiratory rate and heart rate) documented 15 minutes (± 5 minutes) after randomization.

For all randomized subjects, daily vital sign assessments (body temperature, respiratory rate, and heart rate) must be performed at 0800 hours (\pm 2 hours) from Study Day 3 to the completion of Study Day 7.

Sustained heart rate $<$ 100 bpm for \geq 20 seconds must be noted as an AE of bradycardia in the study eCRF.

In this study, a sustained apnea event is defined as lasting \geq 20 seconds and is coincident with at least one of the following: (1) HR $<$ 100 bpm, (2) desaturation (oxygen saturation $<$ 80%), (3) requirement for intermittent positive pressure breaths using inflating pressures above the set CPAP pressure administered manually or mechanically through any patient interface.

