7.1.3 Pulse Oximetry

SpO₂ will be monitored continuously from the time of randomization until completion of Study Day 7.

Sustained SpO₂ $<$ 80% for \geq 20 seconds must be recorded as an AE in the study eCRF.

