6.4 ADVERSE EVENTS

All AEs will be coded by preferred term and system organ class (SOC) from the Medical Dictionary for Regulatory Activities (MedDRA), version 16.1 or above, and will be reviewed by the medical monitor or designee. All AEs will be summarized as categorical variables (frequency and percent) by treatment group unless otherwise indicated. AEs that are related to the device (ADEs) will be summarized with all AEs and separately. AEs will not be compared between treatment groups.

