6.4.3 Other AEs

AEs, other than those listed above, will be summarized by the MedDRA preferred term and SOC for all AEs, regardless of relationship to study drug, and for AEs at least remotely related. If an AE occurs multiple times for the same subject within the same term or body system, only the most severe occurrence for that term or body system will be counted.

In addition, all AEs will be summarized by severity (mild, moderate, severe), relationship to the study drug (unrelated, unlikely related, possibly related, definitely related), whether or not the AE was device related, gender, race, and ethnic origin.

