11 LIST OF TABLES

Table	Title
1.1	Subject Disposition – Study Populations – All Subjects
1.2	Subject Disposition – Study Completion/Termination Status – All Subjects
1.3	Subject Disposition – Protocol Deviations/Violations – All Subjects
2.1	Subject Demographics – Intent-to-Treat Population
2.2	Medical Information – Maternal History – Intent-to-Treat Population
2.3	Medical Information – Birth History – Intent-to-Treat Population
3.1	Concomitant Medications – Safety Population
3.2	Number of Treatments Received – Safety Population
4.1.1	Exploratory Efficacy Analysis – Early Worsening of Respiratory Status Criteria – Intent-to-Treat Population
4.1.2	Exploratory Efficacy Analysis – Late Worsening of Respiratory Status Criteria – Intent-to-Treat Population
4.2	Exploratory Efficacy Analysis – BPD and Survival Without BPD at 36 Weeks PMA – Intent-to-Treat Population
4.3	Exploratory Efficacy Analysis – Time until Intubation for Mechanical Ventilation – Intent-to-Treat Population
4.4	Exploratory Efficacy Analysis – Time until Any Intubation – Intent-to-Treat Population
5.1	Investigational Device – Technical Performance – Safety Population
5.2	Investigational Device – Early Termination of Treatment – Safety Population
6.1	Peri-Dosing Adverse Events – Safety Population
6.2	Air Leak – Safety Population
6.3.1	Treatment-Emergent Adverse Events by System Organ Class and Preferred Term – Safety Population
6.3.2	Treatment-Emergent Adverse Events by System Organ Class, Preferred Term, and Severity – Safety Population
6.3.3	Treatment-Emergent Adverse Events by System Organ Class, Preferred Term, and Relationship – Safety Population
6.3.4	Treatment-Emergent Adverse Events by Severity and Relationship to Study Drug – Safety Population
6.3.5	Treatment-Emergent Adverse Events in Descending Order by Total Active Group – Safety Population
6.4.1	Serious Adverse Events by Preferred Term Displayed in Descending Order by Total Active Group – Safety Population
6.5.1	Adverse Device Effects by Treatment Group – Safety Population
6.6	All-Cause Mortality – Safety Population

- 7.1.1 Clinical Assessments – Vital Signs – Body Temperature – Observed Values and Change from Baseline – Safety Population
- 7.1.2 Clinical Assessments – Vital Signs – Respiration Rate – Observed Values and Change from Baseline – Safety Population
- 7.1.3 Clinical Assessments – Vital Signs – Heart Rate – Observed Values and Change from Baseline – Safety Population

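### SAP 6.4.3 selects repeated adverse events by severity and gives no rule for the relationship tables, so a related non-serious event can be shown as unrelated

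*SAP*

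**What the plan says.** SAP 6.4 sets the general format: "All AEs will be summarized as categorical variables (frequency and percent) by treatment group unless otherwise indicated".

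The first paragraph of SAP 6.4.3 does three things.
- It sets the scope: "AEs, other than those listed above, will be summarized by the MedDRA preferred term and SOC for all AEs".
- It promises two versions of that summary: "regardless of relationship to study drug, and for AEs at least remotely related".
- It ends with the rule for an event that recurs in the same infant: "only the most severe occurrence for that term or body system will be counted".

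The second paragraph then adds summaries of all AEs by severity, by "relationship to the study drug (unrelated, unlikely related, possibly related, definitely related"), by device relationship and by demographic factors. It does not repeat, change or suspend the counting rule.

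The table list in SAP section 11 includes Table 6.3.3, "Treatment-Emergent Adverse Events by System Organ Class, Preferred Term, and Relationship", and Table 6.3.4, which crosses severity with relationship. No table is titled as the related-AE summary. The listings cover violations and deviations, deaths, serious AEs, early termination, medications, ventilation and oxygen. None covers all AEs.

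For bradycardia, Protocol 7.1.1 says that a sustained event "must be noted as an AE of bradycardia in the study eCRF". For desaturation, Protocol 7.1.3 says that it "must be recorded as an AE in the study eCRF". SAP 6.4.1 reports peri-dosing bradycardia and desaturation by incidence and also includes them with all AEs.

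**The concern.** Keeping the worst occurrence is the natural rule for a severity table. It is the wrong one for a relationship table, where the question is whether an infant had any event attributed to the drug. Suppose an infant has a mild, possibly related event some hours after dosing and a severe, unrelated event of the same term on Day 5. Selection by severity keeps the Day 5 event, and the infant is shown only as unrelated. At body-system level any more severe unrelated event in that system has the same effect.

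The error runs one way. Compared with counting every infant who had at least one related occurrence, selection by severity can lower the related count but cannot raise it.

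This matters because Protocol 6.2 bases failed tolerability on AE analysis, with particular interest in events related to administration. The secondary objective also takes the maximum tolerated dose from the safety evaluations within each dosing group.

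**Working it through.** The documents give no figure on this point, so there is none to reproduce. The check is a reading of the text, followed by an illustration of size.

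**1. What the text fixes.**
- In the first paragraph of 6.4.3, the one-occurrence rule and the related-AE summary stand together. The order of operations is missing. If AEs are filtered on relationship first, no infant with a related event is lost. If the worst occurrence is chosen first, some can be.
- The relationship summaries are in the second paragraph. Either the rule carries over, and related events can be displaced, or it does not, and those tables have no rule for repeats. An infant could then be counted in several relationship categories. A rule is needed in either case.
- The cut-off in "regardless of relationship to study drug, and for AEs at least remotely related" is not a category on the SAP's relationship scale or on the scale in Protocol 9.1.1.

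**2. Effect of one infant.** SAP 2.2.3 plans 8 active infants per dose: 1/8 = 12.5 percentage points for the term or body system concerned. Over all 32 active infants: 1/32 = 3.1 points.

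**3. Chance of displacement.** Take one related and one unrelated occurrence of the same term, with severities independent and drawn from the same mix (p1, p2, p3) of mild, moderate and severe.
- P(tie) = p1² + p2² + p3²
- P(related event strictly milder) = (1 − P(tie)) / 2
- If 3 of 8 infants have such a pair, P(at least one displaced) = 1 − (1 − P(strictly milder))³

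For 70/20/10%: tie = 0.49 + 0.04 + 0.01 = 0.54; strictly milder = 0.46/2 = 0.23; at least one of three = 1 − 0.77³ = 0.54.

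| Assumed mix (%) | Strictly milder | Tie | At least one of 3 infants |
|---|---|---|---|
| 33/33/33 | 0.33 | 0.33 | 0.70 |
| 50/30/20 | 0.31 | 0.38 | 0.67 |
| 70/20/10 | 0.23 | 0.54 | 0.54 |
| 90/8/2 | 0.09 | 0.82 | 0.25 |

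With more competing unrelated events, as is likely at body-system level, the chance of displacement rises. Enumerating the same four mixes gives 0.17 to 0.48 with two unrelated events and 0.25 to 0.58 with three.

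The tie column matters because the SAP has no tie-break. When most events are mild, programming rather than the plan decides which of two equal occurrences is kept.

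**4. What remains visible elsewhere.**

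| Type of event | Other output |
|---|---|
| Serious AEs | Listed with every occurrence and its relationship (SAP 6.4.4, Listing 2.2) |
| Device effects | Separate summary (SAP 6.4, Table 6.5.1) |
| Air leaks | Table 6.2, and again in Table 7.8 |
| Peri-dosing bradycardia, desaturation, vomiting | Table 6.1 |
| Other related non-serious AEs | No separate output |

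The peri-dosing window is 2 hours in the SAP executive summary and study schedule but 24 hours in SAP 1.2.3, so the reach of Table 6.1 depends on which applies.

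**The case against.** The strongest reply is that the SAP never says the rule governs the relationship tables. It closes one paragraph, and the relationship summaries open the next as an addition. This stands: displacement is a possible result, not a stated one. It does not remove the gap, since without the rule those tables have no instruction for repeats.

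A second reply is that safety decisions do not rest on these tables. This also stands. Under Protocol 6.1 and 13.2 the SRC reviews all AEs at each dose step, and the enrollment hold in Protocol 6.2 counts infants with related serious AEs. The study has no hypothesis test, and the database keeps every record.

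Three stronger readings are tempting, and the documents do not support them.
- *Half of related events are lost when one unrelated event competes.* That needs random tie-breaking, which the SAP does not specify. The rule itself gives 0.09 to 0.33 under the mixes above.
- *Air leaks drop out because 6.4.3 excludes events listed earlier.* They have Tables 6.2 and 7.8, and the second paragraph of 6.4.3 covers all AEs. At most the wording affects the plain term and body-system summary.
- *The percentage of infants affected saturates and hides episode burden.* The yes/no form for peri-dosing events comes first from 6.4.1. No episode rate is given. At an assumed 0.5 episodes per infant-day, 1 − exp(−rate × time) is 4% over 2 hours and 63% over 48 hours; doubling the rate gives 8% and 86%. Neither window is saturated. Nor do Protocol 7.1.1 and 7.1.3 guarantee one record per episode: Protocol 9.1.3 asks for a diagnosis where signs share a cause and leaves the detail to separate completion guidelines.

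**Conclusion.** The point holds as a gap in the counting rule. SAP 6.4.3 selects repeats by severity and says nothing about which occurrence represents the infant in the relationship tables. If the rule is applied there, infants with a related non-serious AE can appear only as unrelated, and no planned all-AE listing would show it.

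The chances of displacement rest on assumed severity mixes and on severity being independent of relationship; neither comes from the documents. The 12.5-point step rests only on the planned 8 infants per dose.

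The exposure is confined to related non-serious AEs in the final tables. Dose-step reviews, the hold rule and the serious-AE listing are unaffected. It should be corrected before database lock, but it does not put the safety evaluation as a whole in doubt.

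**What to change.** In SAP 6.4.3:
- Severity tables count the most severe occurrence per infant.
- Relationship tables count the occurrence with the strongest relationship, chosen separately at preferred-term and body-system level. For Table 6.3.4, state which attribute selects the occurrence and how ties are broken.
- The related-AE summary filters on relationship before selecting, with its cut-off expressed in the categories of the relationship scale.

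In SAP section 11, add a listing of all AEs with severity and relationship.

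Optionally, where the eCRF holds one record per episode, report the number of bradycardia, desaturation and sustained apnea episodes per infant over 0 to 48 hours in both arms, beside the percentages. SAP 6.4.1 would need the same addition.

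The cost is a few sentences and one listing, plus one table if the option is taken. The main change needs no new data and no change to sample size or conduct. Related-AE counts may look slightly less favourable.

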6.4.4 Serious Adverse Events

All SAEs will be listed and summarized using frequency counts and percentages. If the same SAE occurs multiple times for the same subject, the most severe occurrence will be counted. For this study, unexpected adverse device effects (UADEs) will be analyzed as SAEs.

SAEs, including multiple occurrences, will also be listed, to include severity, relationship to the study drug, gender, race, and ethnic origin.

6.4.5 Deaths

The all-cause mortality during the study will be summarized by treatment group using frequency counts and percentages. Deaths by subject will also be listed and will include primary cause, date and time of death, gender, race, and ethnic origin.

6.5 CLINICAL ASSESSMENTS OF SAFETY

6.5.1 Vital Signs

Vital signs, including body temperature, respiration rate, and heart rate, will be summarized at all pre-specified time points. Clinically significant vital signs will also be recorded as AEs.

6.5.2 Physical Examination

For each body system evaluated at screening and at the final physical examination, frequency counts and percentages of normal and abnormal results will be summarized. In addition, a shift table to describe the changes in normal/abnormal results between screening and the final visit will be presented. Any new abnormal physical examination findings must be documented as AEs.

6.5.3 Electrolytes

Sodium, chloride, potassium, and total carbon dioxide (CO₂) will be summarized at 24 hours post randomization as continuous variables. Clinically significant values will also be recorded as AEs.

6.5.4 Gastric Liquid Volume

Gastric liquid volume will be summarized at 30 minutes following treatment (for active treatments) or randomization as a continuous variable.

6.5.5 Defecation

The number of stools occurring within 24 hours from the time of randomization will be summarized as a discrete variable using frequency and percent.

6.5.6 Respiratory Parameters

Observed and change from baseline values for FiO_2 , PCO_2 , and SpO_2 over 72 hours will be summarized using n, mean, SD, median, minimum, and maximum. In addition, figures for observed values and change from baseline values will be produced.

6.5.7 FiO_2 and Respiratory Support

nCPAP settings at all pre-specified time points will be summarized as continuous variables. For subjects receiving mechanical ventilation (MV) through Day 7, the initial mean airway pressure (MAP), the mode, the respiratory rate, and FiO_2 will be summarized. For subjects receiving supplemental oxygen through Day 7, the initial mode and the FiO_2 will be summarized. All MV and supplemental oxygen data will be listed by subject.

The number of subjects requiring respiratory support in the delivery room will be summarized using frequency and percent.

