 - e) Serum electrolyte measurements
 - f) Body weight
 - g) Gastric liquid volume
 - h) Defecation
12. Chest radiography prior to non-emergent intubation, or in cases of worsening respiratory status, if such a procedure does not delay or compromise the emergent care of the subject
- Extended Observation Period (Day 3 until Day 7):
 1. Survival
 2. Incidences leading to withdrawal from study
 3. Incidence of worsening respiratory status
 4. AEs, including ADEs
 5. Complications of prematurity
 6. Concomitant medication
 7. Assessment of the following:
 - Vital signs
 - O₂ saturation values
 - FiO₂ values through 72 hours
 - PCO₂ values through 72 hours
 8. Chest radiography prior to non-emergent intubation, or in cases of worsening respiratory status, if such a procedure does not delay or compromise the emergent care of the subject.
 9. Use of respiratory support and supplemental oxygen
 - Final Observation Period (Day 8 to 36 Weeks PMA or discharge):
 1. Survival
 2. Incidences leading to withdrawal from study
 3. Incidence of worsening respiratory distress
 4. AEs, including ADEs
 5. Physical exam findings

6. Concomitant medications
7. Use of respiratory support and supplemental oxygen
8. Complications of prematurity

Efficacy Measures
(Exploratory)

1. Technical performance of the ADS
The efficacy of the device delivery of lucinactant for inhalation will be characterized indirectly through the subject's response to treatment and solicited feedback from the principal investigators (PIs) and relevant site-based study staff.
2. Incidence of bronchopulmonary dysplasia (BPD)
3. Rate of survival without BPD at 36 weeks PMA (as applicable)
4. Worsening respiratory status either during or after exposure to lucinactant for inhalation

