3.1.1 Primary Endpoints

The primary endpoints of this study will be derived from the safety evaluations, including adverse device effects (ADEs) reported from the time of randomization until 36 weeks PMA of upon discharge (Section 3.3).

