3.3 Safety Evaluations

The following measures are to be documented in the electronic case report form (eCRF) in accordance with timings outlined in Appendix 2 and Section 7:

1. Survival (date and time of death if applicable)

2. AEs, including ADEs
 - To include: nasal excoriations by examination (≥ 24 hours to ≤ 7 days following aerosol exposure) and evidence of lung air leak (especially pneumothorax) (Section 7.1.8)
 - To be categorized as a peri-dosing events if onset of event is ≤ 2 hours from the time of initiating administration of lucinactant for inhalation [Section 9])
3. Signs consistent with worsening respiratory status (Section 7.5)
4. Concomitant medications (Section 7.3)
5. Use of respiratory support and supplemental oxygen (Section 7.6), to include:
 - Need for endotracheal intubation and mechanical ventilation
 - Need for intermittent positive pressure breaths using inflating pressures above the set CPAP pressure administered manually or mechanically through any patient interface
 - nCPAP and fraction of inspired oxygen (FiO₂) requirements (Section 5.4.1), (Section 7.6.2)
6. Complications of prematurity (ie, IVH, periventricular leukomalacia [PVL], pulmonary hemorrhage, NEC, patent ductus arteriosus [PDA], sepsis, ROP, BPD)
7. Physical examinations (Section 7.1.6)
8. Tolerability of lucinactant for inhalation
9. Incidence leading to withdrawal from study
10. Incidence of air leak
11. Assessments of the following:
 - a) PCO₂ (Section 7.1.5)
 - b) Serum electrolyte measurements (Section 7.1.7)
 - c) Body weight (Section 7.1.2)
 - d) Vital signs (Section 7.1.1)
 - e) Gastric liquid volume (Section 7.1.9)
 - f) Defecation (Section 7.1.10)
 - g) Oxygen (O₂) saturation, as determined by pulse oximetry (SpO₂) (Section 7.1.3)
 - h) Chest radiography, as applicable (Section 7.1.8)

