7.6.3 Documentation During Final Observation Period

From Study Day 8 until the subject completes or withdraws from the study, the following must be evaluated and documented in the study eCRF:

- Intubation and mechanical ventilation: date and time of initiation and discontinuation
- Pressure support (to include nCPAP): date and time of initiation and discontinuation
- Supplemental oxygen: date and time of initiation and discontinuation, mode of delivery and FiO_2
- Intubation: the date and time of intubation for any reason

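### Respiratory support and oxygen use is a safety measure to 36 weeks PMA with start and stop dates collected, but the SAP summarises no duration and reports ventilation and oxygen mainly as settings to Day 7 in infants on that support

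*SAP*

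**What the plan says.** **Endpoint.** Protocol 3.3 lists "Use of respiratory support and supplemental oxygen" among the safety evaluations. Protocol 3.1.1 derives the primary endpoints from those evaluations, "reported from the time of randomization until 36 weeks PMA" or discharge. The protocol summary repeats the measure in each of its three observation periods, the last being headed "Final Observation Period (Day 8 to 36 Weeks PMA or discharge". The SAP Executive Summary names it as a key safety endpoint.

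**Collection.** Protocol 7.6.2 records start and stop times and settings through Day 7. From Day 8, Protocol 7.6.3 asks for "Intubation and mechanical ventilation: date and time of initiation and discontinuation", the same for pressure support including nCPAP, and "Supplemental oxygen: date and time of initiation and discontinuation, mode of delivery" with FiO2.

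**Analysis.** SAP 6.5.7 plans the following:
- Ventilation: "For subjects receiving mechanical ventilation (MV) through Day 7, the initial mean airway pressure (MAP), the mode, the respiratory rate" and FiO2.
- Oxygen: "For subjects receiving supplemental oxygen through Day 7, the initial mode and the" FiO2.
- nCPAP settings at the scheduled times.
- A count of infants needing support in the delivery room.

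For the remainder, "All MV and supplemental oxygen data will be listed by subject". The corresponding outputs are Tables 7.6.1, 7.6.2 and 7.7 and Listings 4.1 and 4.2.

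**The concern.** A safety measure described as use of support should tell the reader how many infants needed each kind and for how long. The two main summaries in SAP 6.5.7 do neither directly. They describe settings among infants who were put on the support, and being put on it can itself depend on treatment. A difference in mean airway pressure between a dose group and control could reflect the treatment, or simply which infants ended up ventilated. Duration, which the collected dates are well suited to give, is left out. An infant ventilated briefly and one ventilated for weeks contribute the same first setting.

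**Working it through.** The plan gives no figure to reproduce here. The check sets what is collected beside what is summarised, then sizes the window.

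**1. Collected versus summarised**

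| Support | Collected from Day 8 (Protocol 7.6.3) | By-group summary to Day 7 | By-group summary after Day 7 | Duration | Listing |
|---|---|---|---|---|---|
| Mechanical ventilation | Start, stop | Settings in ventilated infants (6.5.7, Table 7.6.1); intubation count and time, ITT (4.3.3) | Intubation count and time only | None | 4.1 |
| Pressure support, including nCPAP | Start, stop | nCPAP settings (Table 7.7); high nCPAP and positive-pressure breaths as worsening criteria, to 7 days after birth (4.3.2) | None | None | None planned |
| Supplemental oxygen | Start, stop, mode, FiO2 | Mode and FiO2 in infants on oxygen (Table 7.6.2); FiO2 over 72 hours (6.5.6) | None directly; BPD at 36 weeks (4.3.1) | None | 4.2 |

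The duration column is empty in every row. Appendix 2 of the protocol, footnote 7, says that from Day 8 only start and stop times are recorded for ventilator and pressure support. For those supports the late data can therefore show occurrence and duration and little else.

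**2. Share of the window before Day 7**

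Inputs: entry at 26 weeks 0 days to 28 weeks 6 days (Protocol 1), and follow-up to 36 weeks PMA at most.
- 36w0d = 36 × 7 = 252 days; 26w0d = 26 × 7 = 182; 28w6d = 28 × 7 + 6 = 202.
- Longest window: 252 − 182 = 70 days. For the most mature infant: 252 − 202 = 50 days.
- Share covered by Day 7: 7/70 = 10%; 7/50 = 14%.

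These are counted from birth; randomisation follows within 20 hours. The share is larger for an infant who dies, is discharged or is transferred earlier.

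**3. Conditioning**

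Each active group has 8 infants. If, as an illustration only, 4 were ventilated, the ventilation settings for that group would rest on 4 infants selected by their course after randomisation. The selection could make a group look sicker or healthier; the documents do not indicate the direction.

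**4. Why duration carries the information**

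Inclusion criterion 6 requires every infant to be on nCPAP with FiO2 of 0.25 to 0.50. Almost all infants will therefore count as ever on nCPAP and ever above room air, and what can differ between groups is how long. For ventilation the count is informative, but alone it treats 1 day and 40 days (illustrative values) alike.

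**5. Population**

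Tables 7.6.1, 7.6.2 and 7.7 use the safety population, which SAP 6.1 defines by receipt of study medication. Read literally, that leaves out the nCPAP-only controls.

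**The case against.** The strongest reply is that SAP 6.5.7 should not be read alone. SAP 4.3.3 counts infants intubated for ventilation or for any reason and summarises time to intubation, in the ITT population and with no Day 7 limit. SAP 4.3.2 covers worsening status, 6.5.6 gives FiO2 over 72 hours without restriction to one type of support, and 4.3.1 gives BPD and survival without BPD at 36 weeks. Protocol 13.1 promises summary statistics for all variables, and Protocol 6.1 gives the safety committee summary tables of all safety endpoints.

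Much of this stands, and it rules out several stronger readings:
- A reader might infer that the SAP has no summary of support free of selection. The ITT intubation count is one. If treatment kept milder infants off the ventilator, that count would show it beside the settings table, so one cannot say that benefit would be reported as harm.
- A reader might infer that the remaining 86% to 90% of follow-up has no summary at all. SAP 4.2 runs the efficacy endpoints to study completion, and BPD is assessed at 36 weeks. SAP 1.2.4.1 stops at Day 7, so the two sections should be aligned, but this does not support a blanket claim.
- A reader might fault the plan for not comparing the arms. No formal comparison is planned for any endpoint, so the gap is a missing descriptive summary.
- A reader might infer that all ventilation and oxygen values are first values. The word initial may govern only airway pressure and oxygen mode.

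What the reply does not supply is duration. Time to intubation is given as a mean and median, with no stated place for infants never intubated. The general promise in Protocol 13.1 names no duration variable, and Protocol 13 refers to the SAP for the full set of planned analyses. Deriving durations from listings works at best for ventilation and oxygen, because no listing covers pressure support.

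**Conclusion.** The point holds in limited form. For a listed safety measure running to 36 weeks PMA or discharge, the SAP plans no by-group summary of the duration of ventilation, pressure support or oxygen. After Day 7 it has only intubation count and time, plus BPD at 36 weeks. The dedicated ventilation and oxygen tables describe a subgroup formed after randomisation, within at most 10% to 14% of the window for an infant followed to 36 weeks.

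This assumes that the SAP text and its output list are the full set of planned analyses, and that 4.3.3 runs to study completion as 4.2 states. If the Day 7 limit in 1.2.4.1 applied instead, BPD would be the only summary left after Day 7. No bias is shown to occur, and no sample size or error rate is affected. The change is worth making before database lock because the data are already collected.

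**What to change.** In SAP 6.5.7 and Tables 7.6.1 and 7.6.2, add by treatment group, for all randomised infants including nCPAP-only controls:
- Number and percent ever receiving mechanical ventilation, pressure support and supplemental oxygen. Separate nCPAP from other pressure support where the eCRF allows, since all infants enter on nCPAP.
- Days on, or days alive and free of, each support, from randomisation to Day 7 and to 36 weeks PMA or end of follow-up.
- The rule for deaths and for discharge or transfer before 36 weeks, for example days observed together with the number still followed.
- Whether oxygen given through nCPAP or a ventilator counts towards oxygen days.

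Add a by-subject listing for pressure support. Keep the settings summaries as secondary description with their denominators, and say which values are initial. Align SAP 1.2.4.1 with 4.2 on the end of the evaluation period.

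The cost is SAP wording, a few table rows and one listing. No new data are needed, although durations will be incomplete for infants who leave before 36 weeks. All summaries remain descriptive.
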